## **7. DATA SAFETY AND MONITORING PLAN**

In order to ensure the safety of our subjects, we have taken the following general precautions:

1. All research project personnel have completed training in the protection of human research participants per DHHS guidelines;
2. Oversight from different regulatory bodies such as IRBMED and MCRU Advisory Council will be obtained prior to initiation of the study.
3. Adverse event (AE) and serious adverse event definitions are included in the protocols. Grading and Attribution Scales are also listed in the protocol as above.
4. A plan for unexpected adverse event (AE) and serious adverse event (SAE) reporting is included in the protocol as above.
5. The following entities will be notified in case of any unexpected AE and SAE: IRBMED, MCRU, MDRTC, National Institutes of Health (NIH) and the FDA.
6. We plan to submit an annual report of all adverse events (AE) to the IRB, MCRU, MDRTC and US NIH.
7. An independent Study Monitor will review safety data for this study. [name] has accepted to act as Study Monitor. The Monitor will review anonymous data every year. Patient data will be provided with case numbers. In addition, the Monitor will review all the SAEs. If there is a reason to stop therapy in a particular patient, the Monitor will direct the Principle Investigator. Also, the Monitor may decide to halt this study if there is a pattern of SAEs.

### **7.1 STUDY MONITORING PLAN**

Since the primary investigator also acts as the study sponsor for this clinical research trial, the primary investigator or designee(s) will conduct periodic audits of all research subjects' medical records, laboratory records, source documents, case report forms and informed consent documentation for each patient at the clinical research site. These audits will also review the regulatory submissions for the research trial as well as any other administrative issues that the primary investigator/study sponsor or designee(s) feels warrant inspection for the proper implementation and conduct of the clinical research study.

This monitoring will occur twelve months after the first patient has initiated the protocol, and continue on a yearly basis. Study monitoring will also be conducted on an annual schedule once all study subject activity has been completed for the research trial.

Monitoring of the investigational drug (Metreleptin) will be conducted by the primary investigator/study sponsor or designee(s) during the clinical research trial. This monitoring will occur at the University of Michigan Investigational Pharmacy Services (IDS) located in the University of Michigan Hospital Pharmacy. Investigational drug monitoring will occur at least once every six months while study subjects are receiving study medication. A final investigation drug monitoring will occur once all subjects have completed the protocol and all investigational drug supply has been returned to IDS or otherwise accounted for.

Study monitoring and investigational drug monitoring can occur at a more frequent schedule or for case if the primary investigator/study sponsor deems so necessary. A record of this monitoring will be kept in the study regulatory binder and will be reported to the U of M IRBMED as an ORIO along with the research trial's annual schedule continuing review.

In addition, regulatory agencies may conduct a regulatory inspection. If such an inspection occurs, the primary investigator/study sponsor agrees to notify the University of Michigan IRBMED upon notification by the regulatory agency. The primary investigator/study sponsor agrees to allow the inspector direct access to all relevant documents and to allocate his or her time and that of the protocol-site personnel to the inspector to discuss findings and any relevant issues. The primary investigator/study sponsor will allow University of Michigan IRBMED personnel to be present as an observer during a regulatory inspection, if requested.

## APPENDIX

Protocol Table 1: Schedule of Study Procedures			
Studies	Baseline	Follow up visits (occurring at six month intervals)	Unscheduled visit***
Fasting biochemistry	X	X	X
Fasting adipocytokines	X	X	X
Fasting appetite regulators	X	X	X
Leptin sampling	X	X	X
Metabolomics sample	X	X	X
HOMA-IR	X	X	X
Weight, Height, and Vitals	X	X	X
Study medication distribution and accountability	X	X	X
Leptin (mg/kg/day)	5.0 – 10.0 mg/day	5.0 – 10.0 mg/day	5.0 – 10.0 mg/day
***Study procedures may be omitted at investigator's discretion during unscheduled visits.

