## 2.2 INCLUSION AND EXCLUSION CRITERIA

### *Inclusion criteria for initial phase of the study:*

- Previously completed study protocol:
  - CLINICAL PROTOCOL to investigate the efficacy of recombinant human leptin (METRELEPTIN) in nonalcoholic steatohepatitis (NASH) or nonalcoholic fatty liver disease (NAFLD) associated with lipodystrophy, MB002-014 (IRMBED: HUM00058708)
- Demonstrates clinical benefit as defined by meeting at least one of the following criteria upon completion of the above stated protocols:
  - Reduction of HbA1c  $\geq$  1.0% or,
  - Reduction of triglycerides  $\geq$  30% of baseline or,
  - Decrease in insulin requirements  $\geq$  40% or,
  - Reduction in total NASH score by  $\geq$  2 points,
  - Significant worsening of metabolic parameters after discontinuation of Metreleptin if discontinuation has been undertaken.
  - A health condition that appears to have significantly improved by metreleptin for which two independent health care providers make a request to prevent drug discontinuation. In addition, the PI has to document absence of contraindications for drug continuation (such as bone marrow suppression).
- Is male or female  $\geq$  5 years old at baseline.
- Is male, female not of childbearing potential, or meets all the following criteria if female of childbearing potential (including perimenopausal women who have had a menstrual period within one year):
  - Not breastfeeding
  - Negative pregnancy test result (human chorionic gonadotropin, beta subunit [ $\beta$ hCG]) at baseline (not applicable to hysterectomized females).
  - Must practice and be willing to continue to practice appropriate birth control (defined as a method which results in a low failure rate when use consistently and correctly, such as implants, injectables, oral contraceptives, some intrauterine contraceptive devices, sexual abstinence, tubal ligation, or a vasectomized partner) during the entire duration of metreleptin treatment.
- Has physician-confirmed lipodystrophy as defined by evidence of partial (limbs) loss of body fat outside the range of normal variation.
- If  $\geq$  18 years of age, is able to read, understand and sign the U of M IRBMED approved informed consent form (ICF), communicate with study physician and study team, understand and comply with protocol requirements.

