### *Study Inclusion:*

Criteria for continuation into the long-term phase is based solely on proven clinical benefit using criteria universally accepted to be beneficial. The following criteria are accepted as evidence of substantial clinical benefit upon completion of CLINICAL PROTOCOL to investigate the efficacy of recombinant human leptin (METRELEPTIN) in nonalcoholic steatohepatitis (NASH) or nonalcoholic fatty liver disease (NAFLD) associated with lipodystrophy, MB002-014 (IRMBED: HUM00058708):

- Reduction of HbA1c  $\geq$ 1.0% or,
- Reduction of triglycerides  $\geq$ 30% of baseline or,
- Decrease in insulin requirements  $\geq$ 40% or,
- Reduction in total NASH score by  $\geq$ 2 points.
- Significant worsening of metabolic parameters after discontinuation of Metreleptin if discontinuation has been undertaken.

- A health condition that appears to have significantly improved by metreleptin for which two independent health care providers make a request to prevent drug discontinuation. In addition, the PI has to document absence of contraindications for drug continuation (such as bone marrow suppression).

*Study group:* We will enroll up to a total of up to 15 subjects to receive study drug Metreleptin from our parent studies.

*Restorative leptin therapy:* This is defined as administration of recombinant methionyl-human leptin subcutaneously to achieve high normal levels of circulating leptin in individuals who started out with lower than normal or low normal levels of circulating leptin(1, 2). Recombinant human leptin will be provided by Amryt Pharma (Boston, MA). Previous experience from patients with lipodystrophy or with congenital absence of leptin indicates that this goal can be achieved by administration of 0.02 to 0.10 mg/kg/day in adult males depending on baseline leptin concentrations and body surface area of the patients. In this study, patients will be treated with 2.5 and 5 mg /day (male and female respectively) to achieve high physiological concentrations. Higher dose titrations can be used in the judgment of the PI as indicated up to 10 mg daily. It is important to note that the patients enrolling in this long term study will be on metreleptin therapy that has been found effective, therefore, their dose will likely not change during this protocol. .

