*Treatment:* Up to fifteen patients will be enrolled into this long-term treatment extension study. Patients will be continued on metreleptin treatment as mentioned. This will be injected subcutaneously after reconstitution once a day in the morning at approximately the same time of the day that fits the subject's calendar. Dose may be titrated up to 15 mg daily based on metabolic response as needed.

*Follow-up schedule and monitoring:* Scheduled outpatient visits will occur at 6 month intervals. Tolerability will be assessed at each visit. During each visit, patients', weights, BMI, injection site inspection and basic laboratory data (comprehensive metabolic panel (fasting glucose, BUN, creatinine, sodium, potassium, chloride, CO2, calcium, total protein, albumin, total bilirubin, AST, ALT, alkaline phosphatase), fasting insulin, fasting leptin levels, fasting lipid panel (total cholesterol, triglycerides, HDL, LDL)), will be recorded. Throughout the study, lab work for CBC with differential count and creatinine kinase will be obtained at each visit.

Unscheduled visits may occur at more frequently than ever six months in order to follow-up on any adverse event or unanticipated health issues participants may be having.

*Study Termination:* Patient participation will be concluded five years after the patient's baseline appointment. At this time normal follow-up study procedures will be conducted, final drug accountability will be performed and patient will be transitioned to clinical care.

*Preparation for study visits:* Subjects will be asked to refrain from alcohol or tobacco use for 72 hours prior to the visit. They will report to the Research Center after 10 hours of fasting. They will be allowed to consume water overnight prior to the studies.

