**Amryt representative: [name]**

**Sr. Supply Chain Manager**

**Amryt Pharma PLC**

**[contact]**

### 3.3 DRUG DOSAGE AND ADMINISTRATION

Metreleptin will be administered by subcutaneous injection at the doses specified above. Subjects will be instructed by study personnel to reconstitute the medication and self-administer the injections and will perform the first injection under the supervision of study personnel.

The dosing recommendations for Metreleptin are listed below:

Body Weight	Gender	Daily Recommended Metreleptin Dose
≤40 kg	Male	0.06 mg/kg
	Female	
>40 kg	Male	2.5 mg (0.5 mL)
	Female	5.0 mg (1.0 mL)

Initial Metreleptin dose may be adjusted based upon the subject's dose at termination of the two previous studies for reasons of efficacy. Metreleptin dose may be adjusted at investigator's discretion based on clinical response (e.g. inadequate metabolic control or excessive weight loss or tolerability issues). Injections at a single site will have a maximum allowable volume of 2.0 ml. Preferably study medication will be administered at approximately the same time each day. Drug administration will occur once a day (QD). Metreleptin administration may be changed to twice a day (BID) at investigator's discretion based on clinical response (e.g. inadequate metabolic

control, tolerability issues). Dose exceeding 1.0 mL may be administered as two separate injections in order to minimize patient discomfort due to injection volume. Metreleptin dose can be injected into the abdomen, upper arm or thigh region depending on patient preference and comfort. The site(s) of injection will not occur on the limb from which subsequent blood draws will occur that day.

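### Protocol Table 1 lists 5.0–10.0 mg/day for every patient, a range that excludes the 2.5 mg/day stated for males, and its row label uses a different unit from its cells

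*Protocol*

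**What the plan says.** Dose is stated in four places.

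- **Section 2.2, Study Inclusion, paragraph on restorative leptin therapy:** "patients will be treated with 2.5 and 5 mg /day (male and female respectively) to achieve high physiological concentrations". It then adds: "Higher dose titrations can be used in the judgment of the PI as indicated up to 10 mg daily". The same paragraph expects that doses will probably stay as they are, because patients arrive on treatment already found effective.
- **Section 2.2, Treatment paragraph:** "Dose may be titrated up to 15 mg daily based on metabolic response as needed".
- **Section 3.3, dose table:** above 40 kg, males 2.5 mg (0.5 mL) and females 5.0 mg (1.0 mL) daily; at 40 kg or less, 0.06 mg/kg for both sexes. The text below the table adds: "Initial Metreleptin dose may be adjusted based upon the subject's dose at termination of the two previous studies for reasons of efficacy". Later adjustment is left to the investigator.
- **Appendix, Protocol Table 1:** a row labelled "Leptin (mg/kg/day" (the unit in parentheses) with the entry "5.0 – 10.0 mg/day" in each of the three visit columns, for all patients alike.

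Males are eligible: the inclusion criterion begins "Is male or female" and sets a minimum age of 5 years.

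**The concern.** Two statements in the body text agree on a dose for males, and the schedule at the end of the protocol gives a range that does not contain it. The row also contradicts itself, with a per-kilogram label over absolute daily amounts.

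What is at stake is the reference dose. Section 5.7 requires reports of underdose, overdose and medication errors whether or not an event followed, and Section 5.10 requires every overdose to be reported as a serious adverse event. Those classifications need a dose to be measured against. A male on 2.5 mg/day is as recommended under Section 3.3 and below range under Table 1.

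There is also a conditional link to the efficacy outcomes. The primary outcome is percent change in fasting triglycerides and the secondary is percent change in HbA1c, both hypothesised not to change. If a male were moved from 2.5 mg/day to the table's minimum at baseline, his change from baseline would include the effect of a dose step.

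**Working it through.** The table's range is not derived anywhere, so the check is whether it can be rebuilt from the doses in the body text.

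**1. Stated dose against the Table 1 range (5.0 to 10.0 mg/day)**

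| Source | Group | mg/day | Inside the range? |
|---|---|---|---|
| 2.2 | Male | 2.5 | No |
| 3.3 | Male, above 40 kg | 2.5 | No |
| 2.2 and 3.3 | Female (above 40 kg in 3.3) | 5.0 | Yes, at the lower bound |
| 3.3 | 40 kg or less, both sexes | at most 0.06 × 40 = 2.4 | No |
| 2.2, restorative therapy | Upper limit of titration | 10 | Yes, at the upper bound |
| 2.2, Treatment | Upper limit of titration | 15 | No |

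The printed range is reproduced only by pairing the female dose with the 10 mg limit. For males the ratio of the table's lower bound to the stated dose is 5.0/2.5 = 2.

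**2. Is the body text itself in mg?**

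Section 3.3 gives volumes as well: 2.5 mg / 0.5 mL = 5 mg/mL and 5.0 mg / 1.0 mL = 5 mg/mL. Section 3.4 reconstitutes 11.3 mg in 2.2 mL, and 11.3/2.2 = 5.1 mg/mL. The doses above 40 kg are therefore absolute amounts in mg, and 2.5 is not a slip in one place.

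**3. Label against cells**

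The documents give no patient weights, so 40 to 100 kg is assumed.

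- Cells converted to the label's unit: lowest 5/100 = 0.05, highest 10/40 = 0.25 mg/kg/day.
- Cell figures read in the label's unit: lowest 5 × 40 = 200, highest 10 × 100 = 1,000 mg/day.

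The two readings differ by a factor equal to body weight in kg, so label and cells cannot share one unit. The label's unit is in real use elsewhere: Section 2.2 cites 0.02 to 0.10 mg/kg/day in adult males, and Section 3.3 doses the lightest patients per kilogram.

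**4. Weight of one patient**

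At most 15 patients are to be enrolled, so one patient is at least 1/15 = 6.7% of a full sample. The number of males is not stated.

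**The case against.** The strongest defence is that 2.5 mg is only a recommended dose. The initial dose may follow the dose at the end of the earlier studies, and the investigator may titrate upward, so a given man may properly be on 5 to 10 mg/day. This stands as a limit on scope: the conflict does not affect every male. It does not remove the contradiction. The text expects doses to stay much as they were, so a male who enters on 2.5 mg would remain outside the table. Titration could explain a wider range, but not one that leaves out a stated dose at baseline.

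Secondly, Section 3.3 sends the reader to doses given earlier in the text, and Table 1 is a schedule of procedures. A reader might infer that site staff dose from the table and that men will have their dose doubled at baseline. The protocol does not say so, and this would require overriding both the dosing section and the patient's existing dose. The dose step is therefore a conditional risk.

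Thirdly, a reader might take the label literally and infer a many-fold overdose. The documents do not support that, because every cell prints mg/day. At an assumed 70 kg, 5 mg/kg would be 350 mg, or 350/11.3 ≈ 31 vials a day. This part is a labelling error.

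Finally, it might be inferred that protocol-deviation counts or drug accountability turn on this row. The protocol defines no dose-deviation count, and its accountability provisions (vial return, reconciliation logs, pharmacy monitoring) do not refer to the Table 1 range.

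**Conclusion.** The inconsistency is real and can be read directly from intact text. Table 1 excludes the dose that Section 2.2 states for males and Section 3.3 states for males above 40 kg, by a factor of two at the lower bound, and its row label disagrees with its cells.

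Its reach is limited to males actually on less than 5 mg/day. How many there are cannot be determined from the protocol, which gives neither the number of men nor the doses they bring. For those patients there are two incompatible reference doses, and the practical consequence is ambiguity in the underdose, overdose and medication-error reports. That ambiguity does not by itself make either dose an overdose: Section 5.10 also requires the dose to be considered excessive and medically important.

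An effect on the triglyceride or HbA1c change arises only if the table is followed in place of the existing dose. The point deserves correction, but it does not show that the efficacy results are biased. It rests on no numerical assumption except the illustrative body weights in the unit check.

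**What to change.** Reconcile the dose row of Protocol Table 1 with both paragraphs of Section 2.2 and with Section 3.3, so that one consistent dose statement applies throughout, and give the row's label and cells the same unit.

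Pointing Table 1 to an existing section would not be enough, because the body text is not yet consistent: Section 2.2 gives two titration limits (10 and 15 mg daily), and Section 3.3 adds a weight rule that Section 2.2 does not mention. The reconciliation should cover these at the same time. The choice of dose belongs to the investigator-sponsor and is not made here.

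The cost is small: one table row, plus whatever matching wording is needed in Sections 2.2 and 3.3, in a single amendment. Sample size, visits and outcomes are untouched.
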